## **10.4. Appendix 4: Adverse Events: Definitions and Procedures for Recording, Evaluating, Follow-up, and Reporting**

### **10.4.1. Definition of AE**

An AE is any untoward medical occurrence in a patient or clinical study participant, temporally associated with the use of study intervention, whether or not considered related to the study intervention.

NOTE: An AE can therefore be any unfavorable and unintended sign (including an abnormal laboratory finding), symptom, or disease (new or exacerbated) temporally associated with the use of study intervention.

#### **10.4.1.1. Events Meeting the AE Definition**

- Any abnormal laboratory test results (hematology, clinical chemistry, or urinalysis) or other safety assessments (e.g., ECG, radiological scans, vital signs measurements), including those that worsen from baseline, considered clinically significant in the medical and scientific judgment of the Investigator (i.e., not related to progression of underlying disease).
- Exacerbation of a chronic or intermittent pre-existing condition including either an increase in frequency and/or intensity of the condition.
- New conditions detected or diagnosed after study intervention administration even though it may have been present before the start of the study.
- Signs, symptoms, or the clinical sequelae of a suspected drug-drug interaction.
- Signs, symptoms, or the clinical sequelae of a suspected overdose of either study intervention or a concomitant medication. Overdose itself will not be reported as an AE/SAE unless it is an intentional overdose taken with possible suicidal/self-harming intent. Such overdoses should be reported, regardless of sequelae.
- “Lack of efficacy” or “failure of expected pharmacological action” per se will not be reported as an AE or SAE. Such instances will be captured in the efficacy assessments. However, the signs, symptoms, and/or clinical sequelae resulting from lack of efficacy will be reported as AE or SAE if they fulfil the definition of an AE or SAE.

#### **10.4.1.2. Events Not Meeting the AE Definition**

- Any clinically significant abnormal laboratory findings or other abnormal safety assessments which are associated with the underlying disease, unless judged by the Investigator to be more severe than expected for the participant’s condition.
- Medical or surgical procedure (e.g., endoscopy, appendectomy): the condition that leads to the procedure is the AE.
- Situations in which an untoward medical occurrence did not occur (social and/or convenience admission to a hospital).

- Anticipated day-to-day fluctuations of pre-existing disease(s) or condition(s) present or detected at the start of the study that do not worsen.

#### **10.4.2. Definition of SAE**

If an event is not an AE per definition above, then it cannot be an SAE even if serious conditions are met (e.g., hospitalization for signs/symptoms of the disease under study, death due to progression of disease).

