#### 8.1.3.1. Kidney Stone Events and Stone Burden

Parents or legal guardians of participants will provide a 12-month history of stone events (or as applicable for those less than 12 months of age) experienced by the participant at Screening and will report any stone events during the study.

For the purpose of this study, “stone events” are all events that meet one or more of the following criteria:

- **Renal stone requiring medical intervention** (e.g., outpatient procedures such as lithotripsy, or hospitalization and/or inpatient surgical intervention for confirmed stone related pain and/or complications)
- **Stone passage with or without hematuria**
- **Renal colic requiring medication**

Concurrent events will be defined as events occurring within the same 4-week (28-day) window.

Note: Although a change from baseline in the rate of stone events is an efficacy endpoint, stone events will be considered AESIs (Section [10.4.3](#)).

For the purpose of the study, “stone burden” is a term used primarily as a metric for quantifying and qualifying changes from baseline in the overall number and 2-dimensional surface area of renal stones, as observed via kidney ultrasound over the course of the study.

Taken together, the terms stone event and stone burden will be used to derive meaningful quantification and qualification of overall impact of clinical sequelae of renal stones during the course of the trial.

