### 9.2. Sample Size Determination

It is expected that approximately 25 participants will be screened, such that approximately 20 participants will complete the Day 180 assessments.

No formal sample size estimations were performed. A sample size of 20 participants was considered sufficient to provide an initial assessment of the efficacy and safety of nedosiran in pediatric participants (birth to 11 years of age) with PH1, PH2 or PH3 and relatively intact renal function.

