##### **3. Requires inpatient hospitalization or prolongation of existing hospitalization**

In general, hospitalization signifies that the participant has been detained (usually involving at least an overnight stay) at the hospital or emergency ward for observation and/or treatment that would not have been appropriate in the physician’s office or outpatient setting.

Complications that occur during hospitalization are AEs. If a complication prolongs hospitalization or fulfills any other serious criteria, the event is serious. When in doubt as to whether “hospitalization” occurred or was necessary, the AE should be considered serious.

Hospitalization for elective treatment of a pre-existing condition that did not worsen from baseline is not considered an AE. Pre-planned hospitalizations scheduled, prior to signing the ICF, for an elective medical/surgical procedure do not meet this criterion.

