##### **Kidney Stone Events**

Patients with PH are predisposed to the development of multiple and recurrent urinary tract and kidney stones. As participants may enter the study with pre-existing stones, stone events (as defined in Section 8.1.3.1), while being considered in the evaluation of efficacy, will be considered AESI.

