4.1.1.6 Derived Variables

- Change from baseline = value at current time point – baseline value
- Percentage change from baseline = $\left(\frac{\text{value at current time point} - \text{baseline value}}{\text{baseline value}} \right) * 100\%$
- Spot urinary oxalate-to-creatinine ratio = the average of all the spot urinary oxalate-to-creatinine ratio collected at the specific visit.
- Treatment-emergent AE (TEAE) = any AE with an onset date/time on or after administration (including any partial administration) of the first dose of study intervention and until the study completion date from the end of study CRF.
- Body surface area will be calculated using the following formula (DuBois & DuBois, 1916):
$$BSA = (\text{Weight}^{0.425} \times \text{Height}^{0.725}) \times 0.007184;$$
 with weight in kilograms and height in centimeters.
- Body mass index (BMI) will be calculated using the formula: $\text{Weight [kg]} / (\text{Height}^2 [\text{m}^2])$.
- Estimated Glomerular Filtration Rate (eGFR) will be calculated as described in Protocol Section 8.2.6.1.
- Annualized stone event rate will be derived as number of stone events in the exposure period / total number of years exposed.

The number of stone events will be calculated as the number of discrete (non-concurrent) adverse events marked as a Kidney Stone Event on the adverse event CRF. Kidney stone events include renal stone requiring medical intervention, stone passage with or without hematuria, and renal colic requiring medication.

Concurrent events will be defined as events occurring within the same 4-week (28-day) window. For example, renal colic treated with medication on Monday 12 November 2019 followed by stone passage without hematuria on Friday 30 November 2019 is a single (concurrent) stone event (18 days between start and stop of single stone event). Renal colic treated with medication on Monday 12 November 2019 followed by stone passage without hematuria on Wednesday 13 December 2019 is considered two separate stone events (30 days between discrete event one and event two).

- Quality-of-life Questionnaires:

PedsQL

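### The examples in the SAE definition class PH admissions and progression deaths as non-AEs, against the AE, seriousness and stone-event rules, so their SAE status and 24-hour reporting are ambiguous

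*Protocol*

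**What the plan says.** Protocol 10.4.2 opens with a gate: "If an event is not an AE per definition above, then it cannot be an SAE even if serious conditions are met". The bracketed examples that follow are "hospitalization for signs/symptoms of the disease under study, death due to progression of disease". No other examples are given.

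The same section then lists the seriousness criteria. Death is the first, and the third reads "Requires inpatient hospitalization or prolongation of existing hospitalization". It exempts elective treatment of a pre-existing condition that has not worsened, and admissions planned before consent. It also tells sites to class an AE as serious when they doubt whether a hospitalization occurred or was necessary.

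Other sections bear on the same events:

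- Protocol 10.4.1 defines an AE broadly, whether or not it is related to treatment. Protocol 10.4.1.1 counts worsening of a chronic or intermittent condition as an AE and says that "clinical sequelae resulting from lack of efficacy will be reported as AE or SAE if they fulfil the definition".
- Protocol 10.4.1.2 excludes disease-associated laboratory and safety-assessment findings (unless more severe than expected) and day-to-day fluctuations without worsening. It does not exclude clinical events of PH in general.
- Protocol 8.1.3.1 defines stone events to include those needing "hospitalization and/or inpatient surgical intervention for confirmed stone related pain and/or complications". Protocol 10.4.3.1 says that stone events, "while being considered in the evaluation of efficacy, will be considered AESI".
- SAP 4.1.1.6 counts stone events as discrete "adverse events marked as a Kidney Stone Event on the adverse event CRF".

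**The concern.** A site that admits a child with an obstructing stone can find two opposite instructions. Under the AE, seriousness and stone-event rules, the admission is an AE of special interest (AESI) and meets a seriousness criterion. Under the examples in 10.4.2, it is a model case of something that is not an AE and so cannot be an SAE. A death attributed to progression of PH raises the same conflict.

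The classification matters because expedited reporting and the SAE-based stopping rules depend on it. The trial has a single arm, so no control group can show whether a worsening is natural history, lack of effect or harm. Protocol 10.4.4.3 places that judgment in the causality assessment, where underlying disease is weighed as an alternative cause. The examples in 10.4.2 let a site make the judgment earlier and drop the event before causality is assessed.

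**Working it through.** The plan gives no figure for this point to reproduce. On sample size it says "No formal sample size estimations were performed", and it sets no expected SAE rate. The check is therefore a cross-reading, followed by a bound on size.

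**1. Is a PH-related admission or death an AE?** Under Protocol 10.4.1 and 10.4.1.1 it generally is, because it is an unwanted medical event, a worsening of an existing condition, or a consequence of lack of efficacy. The exclusions in 10.4.1.2 do not reach it. The examples in 10.4.2 say it is not an AE, although the gate refers back to those same definitions.

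**2. Is it serious?** By the criteria in 10.4.2, yes, if the child dies or needs inpatient admission that is not covered by the elective or pre-planned exemptions. By the examples, the question is never reached.

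**3. What follows from each classification?**

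| Consequence | SAE | Non-serious AE or AESI | Treated as not an AE |
|---|---|---|---|
| 24-hour report (8.3.1) | yes | no | no |
| Collection for 30 days after participation ends (8.3.1) | yes | no | no |
| Causality assessment (10.4.4.3) | yes | yes | no |
| Required follow-up until resolved, stable or explained (8.3.3) | yes | yes, if an AESI | no |
| Eligible for the SAE criteria in 7.1.1 and 7.1.2 | yes, if their other conditions are met | no | no |
| Stone-event count (SAP 4.1.1.6) | yes, if marked as a stone event | yes, if marked as a stone event | no |

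The examples can move an event from the first column to the second. If the site takes them literally, the event moves to the third.

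Deaths have one further gap. Protocol 9.4.3.2 promises that deaths will be summarized or listed. The AE overview in SAP 4.3.1.2.1 provides only for fatal treatment-emergent AEs, which a death classed as a non-AE would not enter.

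A site that looks for guidance is also misdirected. Protocol 8.3 to 8.3.3 point to Section 10.3 for AE and SAE definitions and procedures, but 10.3 now covers blood volumes.

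**4. Size.** The inputs are the SAE counts in Protocol 2.2.3.1 and the approximately 25 participants to be enrolled (Protocol 1.1).

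- Study 101, PH participants: 4/18 = 22.2%, which matches the stated percentage. 0.222 × 25 = 5.6 children.
- Study 201, nedosiran arm: 1/23 = 4.3%. 0.0435 × 25 = 1.1 children.
- Study 201, both arms: (1 + 2)/(23 + 12) = 3/35 = 8.6%. 0.0857 × 25 = 2.1 children.

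The range is about 1 to 6 of 25 children with an SAE of any cause. The documents do not say what share of SAEs is PH-related, so the number that 10.4.2 could remove cannot be calculated.

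**The case against.** The strongest reply is that 10.4.2 is conditional. It excludes only events that are not AEs under the definitions above it, and those definitions bring worsening disease and the sequelae of lack of efficacy back in. A careful site would reach the right answer. That is fair as a reading of the rule, but the only examples attached to the rule point the other way.

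A reader might infer more than the documents support:

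- *That AESI status contradicts non-SAE status.* It does not. Protocol 8.3.3 provides for non-serious AESIs. The conflict is over whether the event is an AE and whether it is serious.
- *That stone events escape causality review.* Once recorded as AEs they receive causality assessment and follow-up, and the SAP summarizes them as AESIs. They are lost only if a site follows the examples and ignores 8.1.3.1 and 10.4.3.1.
- *That the study pause is disabled.* Protocol 7.1.2 also needs a life-threatening or fatal event that is at least possibly related, and the SAE criterion in 7.1.1 needs relatedness too. A stone admission that is not life-threatening, or a death judged unrelated, would not suspend the study even as an SAE.
- *That the hazard ratio of 3.44 for death in Protocol 2.1 shows such deaths are expected here.* It compares children under 2 with infantile oxalosis against older PH patients with renal replacement therapy. This trial excludes dialysis, transplantation and severe systemic oxalosis.

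Other safeguards exist. Immediate safety concerns go to the Sponsor at once (Protocol 8), the Safety Review Committee meets every 3 months after its first review (2.3.4), and postmortem findings are supplied (10.4.4.4). They lower the chance that a grave event goes unseen, but they do not replace 24-hour SAE reporting.

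**Conclusion.** The contradiction stands and should be fixed. The examples in Protocol 10.4.2 conflict with the AE definition, the seriousness criteria and the stone-event rules. They leave the SAE status and expedited reporting of PH-related admissions and deaths ambiguous. The point applies to children across the whole age range, birth to 11 years.

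The loss depends on a site following the examples, and nothing in the documents shows that any event has been missed. The size is unknown. About 1 to 6 of 25 children might have an SAE of any cause if this trial resembled one of the earlier studies, which differ from it in age and, for Study 101, in giving a single dose. With so few SAEs expected, misclassifying even one would change the reported rate noticeably. Any effect on the stone-event rate falls on an exploratory endpoint. The primary endpoint, a urine ratio, is not affected.

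**What to change.** Delete the bracketed examples in Protocol 10.4.2 and state in their place that:

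1. any stone event as defined in 8.1.3.1 is recorded on the AE form as an AESI;
2. stone events, other PH-related clinical events and deaths that meet the AE definition are SAEs whenever a criterion in 10.4.2 is met, with causality assessed;
3. the existing exemptions for elective and pre-planned admissions remain.

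Notify sites by letter. The same amendment could correct the references to Section 10.3.

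The cost is a few sentences, a letter, some additional SAE reports and a slightly higher reported SAE count. No dose, visit or treatment rule changes. Making every PH admission an SAE regardless of the definitions, or searching source records for past admissions, would go further than the contradiction requires.

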**An SAE is defined as any untoward medical occurrence that, at any dose:**

##### **1. Results in death**

##### **2. Is life-threatening**

The term ‘life-threatening’ in the definition of ‘serious’ refers to an event in which the participant was at risk of death at the time of the event. It does not refer to an event, which hypothetically might have caused death, if it were more severe.

##### **3. Requires inpatient hospitalization or prolongation of existing hospitalization**

In general, hospitalization signifies that the participant has been detained (usually involving at least an overnight stay) at the hospital or emergency ward for observation and/or treatment that would not have been appropriate in the physician’s office or outpatient setting.

Complications that occur during hospitalization are AEs. If a complication prolongs hospitalization or fulfills any other serious criteria, the event is serious. When in doubt as to whether “hospitalization” occurred or was necessary, the AE should be considered serious.

Hospitalization for elective treatment of a pre-existing condition that did not worsen from baseline is not considered an AE. Pre-planned hospitalizations scheduled, prior to signing the ICF, for an elective medical/surgical procedure do not meet this criterion.

##### **4. Results in persistent disability/incapacity**

The term disability means a substantial disruption of a person’s ability to conduct normal life functions.

This definition is not intended to include experiences of relatively minor medical significance such as uncomplicated headache, nausea, vomiting, diarrhea, influenza, and accidental trauma (e.g., sprained ankle) which may interfere with or prevent everyday life functions but do not constitute a substantial disruption.

##### **5. Is a congenital anomaly/birth defect**

##### **6. Other situations**

Medical or scientific judgment should be exercised in deciding whether SAE reporting is appropriate in other situations such as important medical events that may not be immediately life-threatening or result in death or hospitalization but may jeopardize the participant or may require medical or surgical intervention to prevent one of the other outcomes listed in the above definition. These events should usually be considered serious.

Examples of such events include invasive or malignant cancers, intensive treatment in an emergency room or at home for allergic bronchospasm, blood dyscrasias or convulsions that do not result in hospitalization, or development of drug dependency or drug abuse.

### 10.4.3. Definition of Adverse Event of Special Interest

An AESI is a noteworthy event for the particular product or class of products that a Sponsor may wish to monitor carefully (CIOMS VI, 2005).

#### 10.4.3.1. Events Meeting the AESI Definition

##### **Injection site reaction (ISR):**

An ISR is a disorder characterized by an intense adverse reaction (usually immunologic) developing at the site of an injection. Potential ISRs will be graded as follows:

Signs or symptoms at the injection site (e.g., erythema, swelling) with a time to onset of 4 or more hours from the time of study intervention administration will be evaluated according to the Common Terminology Criteria for Adverse Events (CTCAE) v 5.0 criteria for ISR, detailed below. If any of the CTCAE criteria for ISR are met, the event will be recorded as an ISR and graded in accordance with Table 6.

**Table 6: Grading of Injection Site Reactions, CTCAE v 5.0**

Grade 1	Grade 2	Grade 3	Grade 4	Grade 5
Tenderness with or without associated symptoms (e.g., warmth, erythema, itching)	Pain; lipodystrophy; edema; phlebitis	Ulceration or necrosis; severe tissue damage; operative intervention indicated	Life-threatening consequences; urgent intervention indicated	Death

Individual signs or symptoms at the injection site with a time to onset of less than 4 hours from the time of study intervention administration will be recorded as AEs (not as an ISR) and graded in accordance with the intensity categories detailed in Section 10.4.4.2.

##### **Muscle pain or weakness:**

Because the nonclinical safety program in mice identified potential off-target effects on skeletal muscle, participants should be monitored for signs and symptoms of muscle weakness or pain, in addition to measurement of plasma CK.

##### **Kidney Stone Events**

Patients with PH are predisposed to the development of multiple and recurrent urinary tract and kidney stones. As participants may enter the study with pre-existing stones, stone events (as defined in Section 8.1.3.1), while being considered in the evaluation of efficacy, will be considered AESI.

### 10.4.4. Recording and Follow-Up of AE and/or SAE

#### 10.4.4.1. AE and SAE Recording

When an AE/SAE occurs, it is the responsibility of the Investigator to review all documentation (e.g., hospital progress notes, laboratory reports, and diagnostics reports) related to the event.

The Investigator will then record all relevant AE/SAE information in the eCRF.

- It is not acceptable for the Investigator to send photocopies of the participant's medical records in lieu of completion of the AE/SAE eCRF page.

- There may be instances when copies of medical records for certain cases are requested by the Sponsor or Medical Monitor. In this case, all participant identifiers, with the exception of the participant number, will be redacted on the copies of the medical records before submission.

The Investigator will attempt to establish a diagnosis of the event based on signs, symptoms, and/or other clinical information. Whenever possible, the diagnosis (not the individual signs/symptoms) will be documented as the AE/SAE.

#### **10.4.4.2. Assessment of Intensity**

The Investigator will make an assessment of intensity for each AE and SAE reported during the study and assign it to one of the following categories:

- **Mild:** An event that is easily tolerated by the participant, causing minimal discomfort and not interfering with everyday activities.
- **Moderate:** An event that causes sufficient discomfort and interferes with normal everyday activities.
- **Severe:** An event that prevents normal everyday activities.

An AE that is assessed as severe should not be confused with an SAE. Severe is a category utilized for rating the intensity of an event; and both AEs and SAEs can be assessed as severe.

An event is defined as ‘serious’ when it meets at least one of the predefined outcomes as described in the definition of an SAE (see Section 10.4.2), NOT when it is rated as severe.

#### **10.4.4.3. Assessment of Causality**

The Investigator is obligated to assess the relationship between study intervention and each occurrence of each AE/SAE.

A “reasonable possibility” of a relationship conveys that there are facts, evidence, and/or arguments to suggest a causal relationship, rather than a relationship cannot be ruled out.

The Investigator will use clinical judgment to determine the relationship.

Alternative causes, such as underlying disease(s), concomitant therapy, and other risk factors, as well as the temporal relationship of the event to study intervention administration will be considered and investigated.

The Investigator will also consult the IB and/or Product Information, for marketed products, in his/her assessment.

For each AE/SAE, the Investigator must document in the medical notes that he/she has reviewed the AE/SAE and has provided an assessment of causality.

There may be situations in which an SAE has occurred, and the Investigator has minimal information to include in the initial report. However, it is very important that the Investigator always make an assessment of causality for every event before the initial transmission of the SAE data to the SAE Submission Coordinator.

The Investigator may change his/her opinion of causality in light of follow-up information and send a SAE follow-up report with the updated causality assessment.

The causality assessment is one of the criteria used when determining regulatory reporting requirements.

The following definitions will be used in assessing causality:

- **Not Related:** Event for which sufficient evidence exists to conclude that the etiology is unrelated to study intervention.
- **Possibly Related:** There is some temporal relationship between the event and the administration of the study intervention, and the event is unlikely to be explained by the participant's medical condition or other therapies.
- **Probably Related:** The temporal relationship between the event and administration of the study intervention is suggestive and the event is unlikely explained by the participant's medical condition or other therapies.
- **Definitely Related:** The event follows reasonable temporal sequence from administration of the study intervention, follows a known or suspected response pattern to the study intervention, is confirmed by improvement upon stopping the study intervention, and reappears upon repeated exposure, if that occurs.

